8.3. Variables

There are two primary baseline periods of interest from which variables of interests will be evaluated: 1) 12-months fixed pre-index period and 2) a variable length baseline period is the maximal continuous enrollment window prior to index and at least 1-year pre-index. The primary post-index period is 12 months including the index date. Other observation periods are noted below.

Variable	Role	Data source(s)	Operational definition
Demographics (Table 1)		
Age	Baseline Characteristic	All	Age will be defined as of the index year.
Age groups	Baseline Characteristic	A11	Patients will be assigned to one of the following age groups based index age: 18–44, 45–64, and 65yo.
Gender	Baseline Characteristic	All	Gender will be captured from enrollment data.
Insurance type	Baseline Characteristic	All	Whether the patient was covered under a commercial or Medicare Supplemental (Truven DataType) insurance plan will be captured.
Plan type	Baseline Characteristic	All	HMO, EPO, GPO, etc via.
			PlanType.
Geographic region	Baseline Characteristic	All	The United States (U.S.) region in which the study patient is enrolled in a health plan will be determined and reported and states will be categorized into five geographic regions: Northeast, South, Midwest, West, Unknown (https://www2.census.gov/geo/pdfs/maps- data/maps/reference/us_regdiv.pdf).
Variable length baselin	eBaseline Characteristic	All	Identify the duration of variable length (ie, all available pre-index continuous enrollment) baseline period.

Variable	Role	Data source(s)	Operational definition
RA-Related Medication	Use in Pre-Index (Tabl	e 2)	
Pre-index biologic DMARD use	Baseline Characteristic	All	A count of unique (on different days) pharmacy/admin claims on different days for ADA/ETN will be created during the 12 month baseline period.
Time from last pre- index bDMARD to index	Baseline Characteristic	All	A variable for the interval between last ADA/ETN pharmacy/administration claim and index. Stratify by <3 mos, 3-<6 mos and 6-12 mos pre-index.
Time from first pre- index bDMARD to index	Baseline Characteristic		A variable for the interval between first ADA/ETN pharmacy/administration claim during the variable length baseline and index. Stratify by <6, 6-12, ≥12 mos.
Pre-index NB- DMARD use	Baseline Characteristic	All	The use of the 4 main NB- DMARDS (methotrexate- MTX, sulfasalazine-SSZ, hydroxychloroquine-HCQ, and leflunomide- LEF), and the other NB-DMARDS (See codes in Appendix 2) will be identified during the pre-index period. Indicator variables will identify the specific medications (MTX, SSZ, HCQ, LEF and other NB-DMARDs) used during the 12 mos pre-index period. A count will be created to identify the number of different NB-DMARDS during variable length baseline and number of prescriptions/administrations on different days received during the 12-mos pre-index period.

Variable	Role	Data source(s)	Operational definition
RA-Related Medical His	tory (Table 2)	1	
Pre-index hospitalization for RA			0/1 flags will be created to determine if the patient had an inpatient visit (length of stay>1 day) with an RA diagnosis (any claim position) in the 90 days before the index date and in the 12 months before the index date. A separate variable will be created for identifying the number of RA related hospitalizations during the entire 12-month baseline period.
Disease duration	Baseline Characteristic	All	The number of days from the earliest claim with a diagnosis of RA in the variable length baseline until the index date will be identified.
Pre-index Claims based Index of RA Severity (CIRAS)	Baseline Characteristic	Al	The Claims-based Index for RA Severity will be implemented. CIRAS (12) provides a single value of severity using the following 9 measures: age, gender, inflammatory marker tests, rehabilitation visits, Felty Syndrome, platelet orders, rheumatoid factor tests, chemistry panels, and rheumatologist visits (See Appendix 3).
Comorbidities (Table 3)			
	Baseline Characteristic	All	A comorbidity score will be calculated based on the
Charlson Comorbidity Index score			presence of diagnosis codes on medical claims in the 12-months pre-index period. The Quan-Charlson (13) Comorbidity Index (QCCI) score will also be categorized into the following groups: zero, one to two, three to four, and five or more CCI comorbidities.
Comorbidities of interest	Baseline Characteristic	All	 0/1 flags will be created to identify the presence of the following comorbidities during the 12-month baseline period (see Appendix 4). Cardiovascular diseases. Chronic obstructive pulmonary disease (COPD). Asthma. Kidney disease. Diabetes. Depression. Anxiety. Liver disease. Sleep disorders. Hypertension. Hyperlipidemia. Interstitial lung disease.

Variable	Role	Data source(s)	Operational definition
Cumulative OOP Costs pre-index	Baseline Characteristic	All	The total, pharmacy and medical OOP costs (deductible+copay+coinsurance) resource use from January 1 of index year through Index.
Index Date OOP costs	Baseline Characteristic	All	Total, pharmacy (excluding index medication) and medical OOP costs on index date.
Index Medication (Table	4)		
Index Prescriber	Baseline Characteristic	All	Top 5 index medication prescriber specialties and other or unknown will be identified.
Index month/year	Baseline Characteristic	All	The month and year of the patient's index date (start of TOFA, ETN, ADA) will be identified.
Index Medication OOP costs	Baseline Characteristic	All	The index medication pharmacy OOP costs (deductible+copay+coinsurance) will be identified for the first index medication rx and cumulative by month (1-12) of follow-up (only looking at pharmacy claims here noting index event is a prescription fill).
Index combination vs. monotherapy regimen status	Baseline Characteristic	All	Patients with a use of one of the 4 main NB- DMARDs (injectable and oral MTX, SSZ, HCQ, LEF) within 90 days on or after the index date will be considered as being treated with combination therapy regimen, others will be classified as monotherapy. For monotherapy, will evaluate 6-mos pre-index use of each of the four main and other NB- DMARDs. For combination regiment, will stratify by 6 mos pre-index use of the four main and other NB-DMARDs.
Post-Index Treatment Pa	tterns (Table 4)		
Treatment Persistence (5 groups)	Outcome	All	Persistent with the index medication will be defined as not having a gap in therapy of at least 60 days between fills/admins. For retail pharmacy (rx) claims the day supply will be utilized and rounded to the nearest 28-day supply for ETN and ADA and 30- day supply for TOFA. For subcutaneous ETN and ADA administrations, a 28-day supply will be assumed.

Variable	Role	Data source(s)	Operational definition

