7.1. Primary Objectives

To evaluate the impact of (1a) TOFA index prescription OOP costs and (1b) TNFi cycling with etanercept (ETN) and adalimumab (ADA) vs. switching to TOFA on treatment persistence duration (see Section 8.3).

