7.2. Secondary Objectives

To compare patients with (1) high (>median) vs. low (≤median) TOFA index prescription OOP costs, and, (2) TNFi cycling with ETN and ADA vs. switching to TOFA on:

- Differences in demographic and clinical characteristics;
- Treatment patterns including dosing, concomitant medication use, adherence, and switching, and a 6-factor effectiveness proxy (ie, Curtis algorithm) between comparator cohorts;
- Post-index and change (Post-Pre) in All-cause and RA-related health care utilization associated costs.

C

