8.3.1. Health Care Cost and Utilization

All cost and utilization measures will be identified in the 12-month pre-index period and the 12- month post-index period. Claims occurring on the index date will be considered part of the post-index period. Baseline and follow-up costs and the change in 12-month costs from baseline to follow-up will then be examined. Cost measures will comprise the total amount paid by the health plan and patient.

• All-cause health care resource utilization- Medical resource utilization will be calculated for outpatient visits, emergency department (ED) visits, and inpatient admissions and pharmacy utilization will include all paid prescription claims.

• RA-related resource health care utilization.

- Medical resource utilization related to RA will be calculated for outpatient visits, ED visits, and inpatient admissions with an RA diagnosis in any claim position.
- RA-related treatment administrations (with and without a concurrent RA diagnosis) will also be identified by presence of HCPCS codes for ADA, ETN, other TNFI and other advanced therapy; methotrexate or other NB-DMARD; low, medium and high potency orticosteroids; NSAIDS; and strong and weak opioids (*See Appendices Appendix 1, Appendix 2, Appendix 5*).
- Pharmacy utilization will included all paid prescription claims for TOFA, ADA, ETN, another TNFI or alternative MOA; methotrexate, sulfasalazine, leflunomide, hydroxychrolorquine and other NB-DMARDs; low, medium, high potency corticosteroids; NSAIDS; and weak and strong opioids (*See Appendices Appendix 1, Appendix 2, Appendix 5*).

- Health care costs-Health care costs will be computed as the combined health plan and patient paid amounts. Costs will be calculated as total costs, pharmacy/treatment costs, and medical costs. Medical costs will be further broken down into outpatient costs, emergency room costs, and inpatient costs. Costs will be adjusted using the annual medical care component of the Consumer Price Index (CPI) to reflect inflation between 2014 (the earliest start of the pre-index period) and 2017 (the cost of claims occurring in 2018 will not be adjusted).¹⁶

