8.7.4. Multivariate Analysis

To control for possible confounding of the relationship between the outcomes and independent variable of interest, select objectives will be conducted utilizing multivariable methods as described above.

Final outcomes for multivariate analysis will be selected after review of descriptive results. Possible outcomes of interest include: total all-cause health care cost, total RA-related health care cost, cost of bDMARDs/tofacitinib/administration/NB-DMARDS, medication effectiveness (yes vs. no).

For each model, specific predictors to be included will be determined based upon clinical rationale and statistical significance. Variables listed in Section 8.3 will be considered for inclusion in the multivariable models. Additional variables identified throughout the course of the study will also be considered. Following standard procedure, regression diagnostics will be performed for each model to assess goodness of fit and violations of model assumptions (eg, multicollinearity, heteroskedasticity). When there are violations of the model, programmers will note them and make appropriate corrections to the data (ie, typically through transformation of either the independent or dependent variables) or in the method of estimation.

In particular, generalized linear models will be fit, using appropriate distributions and links for the nature of the data (eg, normally-distributed data with identity link, binary data and logit link). Results will be displayed on the original scale (that is, the inverse link). If sufficient sample size, tofacitinib IR and tofacitinib XR will be treated as separate groups. That is, contrast statements will be used to average the two groups when comparing to bDMARDs. Point estimates (that is, mean differences, ratios, odds ratios), 95 percent confidence intervals, and p- values will be presented for contrasts; ANOVA table will be presented to display the strength of the independent variables, including point estimates and p-values.

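### As worded, the pre-index cumulative OOP variable can include the index-prescription OOP that is the objective 1a exposure; adjusting for that version would distort the adjusted OOP effect

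*Combined protocol and SAP*

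**What the plan says.** Objective 1a (Section 7.1) is "To evaluate the impact of (1a) TOFA index prescription OOP costs" on persistence duration. Section 7.2 gives the contrast as "high (>median) vs. low (≤median) TOFA index prescription OOP costs", and Section 8.7.1.1 uses the same split for the descriptive comparison. Section 8.7.1.1 also promises a multivariable analysis, without saying in what form OOP enters it.

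Three rows of the Section 8.3 table carry OOP costs around index:

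- *Cumulative OOP Costs pre-index*: total, pharmacy and medical OOP (deductible, copay and coinsurance), "resource use from January 1 of index year through Index".
- *Index Date OOP costs*: "Total, pharmacy (excluding index medication) and medical OOP costs on index date".
- *Index Medication OOP costs*, the source of the exposure: pharmacy OOP that "will be identified for the first index medication rx and cumulative by month (1-12) of follow-up".

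Section 8.3.1 adds a boundary rule for cost and utilization measures: "Claims occurring on the index date will be considered part of the post-index period". The opening of Section 8.3 also puts the index date in the post-index period, but says that other observation periods are noted in the rows.

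On model building, Section 8.7.4 says: "Variables listed in Section 8.3 will be considered for inclusion in the multivariable models". Selection is by clinical rationale and statistical significance. Section 8.7.2.1 names cumulative and index OOP costs among the characteristics to be evaluated, under an objective meant to inform the multivariable analyses.

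**The concern.** The index event is itself a pharmacy fill. A programmer who sums pharmacy OOP up to and including the index date, with no carve-out, will add the index fill to the cumulative variable. The neighbouring row has that carve-out and this one does not. Same-day medical and other pharmacy OOP would also be counted in both rows.

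If that variable then enters the objective 1a model, the model adjusts the exposure for a sum that contains the exposure. Spending earlier in the plan year is an obvious candidate confounder of index OOP, so its selection is foreseeable. A covariate that contains the exposure may also pass a significance screen because of the exposure. At stake is the adjusted estimate for one half of the primary objective.

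**Working it through.** The plan states no effect size, OOP distribution or sample size, so there is no figure to reproduce. The check is algebra plus an illustration on assumed distributions.

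**Notation.** X = OOP of the index prescription; P = OOP from 1 January of the index year to the day before index; C = P + X, the literal cumulative variable (other same-day OOP ignored). H = 1 if X is above its median. b and g are the per-dollar effects of X and P.

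**Step 1, continuous exposure.** bX + gP = (b − g)X + g(P + X). Adjusting for C instead of P therefore changes the coefficient of X from b to b − g. With b = −1:

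- g = 0: −1 (no bias, only collinearity)
- g = −0.5: −0.5
- g = −1: 0 (full cancellation)
- g = +0.5: −1.5 (inflation)

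**Step 2, high/low split, outcome linear in dollars.** Write Y = gC + (b − g)X. In least squares on H and C, the coefficient of H is (b − g) times the coefficient of H when X is regressed on H and C. Adjusting for P, it is b times the coefficient of H when X is regressed on H and P. Hence

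share retained = (1 − g/b) × k,

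where k is the ratio of those two coefficients of H and equals the share retained when g = 0. If X and P are independent, k = Var(P) / [Var(P) + W], with W the variance of X within the high and low groups.

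**Step 3, numbers (assumed).** X is log-normal with log-SD 1. P has the same shape, multiplied by a scale s.

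- Var(X) = e(e − 1) = 4.671.
- The two halves differ in mean by 2.251, so W = 4.671 − 2.251²/4 = 3.404.
- For s = 1, independent: k = 4.671/(4.671 + 3.404) = 0.578.

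The rows with log-scale correlation 0.5 come from a least-squares simulation with 1,000,000 records. The same simulation reproduced the independent rows to within about one percentage point.

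| Correlation | s | g = 0 (k) | g = 0.5b | g = b | g = −0.5b |
|---|---|---|---|---|---|
| 0 | 0.5 | 26% | 13% | 0% | 38% |
| 0 | 1 | 58% | 29% | 0% | 87% |
| 0 | 2 | 85% | 42% | 0% | 127% |
| 0 | 4 | 96% | 48% | 0% | 143% |
| 0.5 | 0.5 | 10% | 5% | 0% | 15% |
| 0.5 | 1 | 34% | 17% | 0% | 51% |
| 0.5 | 2 | 61% | 31% | 0% | 92% |
| 0.5 | 4 | 80% | 40% | 0% | 120% |

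The split loses effect even at g = 0, because C carries the variation of X within each half. This needs an outcome that varies with dollars within the halves. If the effect were a pure step at the median, g = 0 would give no bias.

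**Step 4, would diagnostics catch it?** With X and P independent and r = SD(P)/SD(X), the variance inflation factor for X given C is 1 + 1/r²: 101 at r = 0.1, 5 at r = 0.5, 2 at r = 1 and 1.25 at r = 2. The general multicollinearity check in Section 8.7.4 would flag the extreme cases and could miss the ordinary ones. For a patient with no OOP earlier in the year, C equals X exactly.

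**The case against.** The best defence is that the three rows form a sensible partition: spending before index, index-day spending other than the index drug, and the index drug itself. On that view the word pre-index in the label already excludes the fill, and no carve-out is needed. Section 8.3.1 agrees if it governs here, since index-date claims are then post-index. This stands as a fair account of what may have been intended. It does not settle the matter: the row sets its own calendar-year window, Section 8.3 allows rows to do so, and the operational wording runs up to index.

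The second defence is that nothing commits the sponsor to adjusting for this variable. This also stands. Section 8.3 lists the exposure and the outcomes as well, so appearing there does not make a variable a covariate. Double counting of same-day OOP matters for modelling only if both rows enter one model.

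Three stronger readings are tempting and are not supported. A reader might infer that the plan definitely places the exposure in the covariate; the label and Section 8.3.1 contradict that. A reader might infer that the primary result will be biased; the adjustment is only possible, and the unadjusted comparison in Section 8.7.1.1 is untouched. A reader might infer that the bias always runs toward no effect, or put a number of days on it; the direction depends on the sign of g, and no OOP distribution or effect size is given.

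**Conclusion.** The point holds as an unresolved definition with a foreseeable consequence. On its literal wording the cumulative variable contains the objective 1a exposure, contrary to its own label and to the index-date rule. If that version is adjusted for, the adjusted OOP effect is distorted. The usual direction is attenuation, and it is complete if earlier and index dollars have equal per-dollar effects. Inflation is possible if earlier OOP goes with longer persistence while index OOP shortens it.

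The continuous result (b to b − g) is exact on the scale of the linear predictor. The percentages for the split rest on least squares, log-normal costs, an outcome linear in dollars, and the chosen scales and correlations; they show a range and do not predict this study. The point is worth correcting before programming, since Section 8.8 has analyses programmed to the protocol's specifications and two programmers could reasonably build different variables.

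**What to change.** Define the cumulative variable as OOP from 1 January of the index year through the day before the index date (zero for a patient indexed on 1 January). Keep same-day OOP other than the index drug only in the *Index Date OOP costs* row. State that any prior-OOP covariate in the objective 1a model excludes the index fill, and say in advance whether that model will include one.

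Excluding only the index fill would also take the exposure out of the covariate, but would leave same-day costs in two rows. Ending the window a day earlier solves both and agrees with Section 8.3.1. The cost is one phrase in the table and one date boundary in the code. No information is lost, because index-day costs keep their own rows.

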8.7.2. Secondary Objectives

8.7.2.1. Explore the Differences in Demographic and Clinical Characteristics Between TOFA Index Prescription OOP Costs and TNFi Cycling with ETN and ADA vs. TOFA Switching Cohorts

For this objective descriptive analysis will be conducted. The goal of this objective will be to describe the respective cohorts and explore the presence of demographic and clinical characteristics differences between the cohorts that will inform multivariable analyses. Known demographic characteristics (eg, age, gender, geographic location) will be summarized. In addition, other patient characteristics (eg, pre-index RA medication use and medical history, comoribidity status, cumulative/index OOP costs) will be evaluated. Index medication prescriber, regimen, and OOP costs will also be described.

8.7.2.2. Compare Treatment Patterns Including Dosing, Adherence, Persistence Treatment Patterns Between TOFA Index Prescription OOP Costs and TNFi Cycling with ETN and ADA vs. TOFA Switching Cohorts

For this objective, treatment patterns will be summarized across the cohorts of interest. Specific treatment patterns include changes in use of concomitant NB-DMARDs, number and proportion of patients in the five treatment persistent groups (persistent, switch immediately, discontinue and switch, discontinue and restart, discontinue and no switch or restart), switch anytime, or effectively treated (meeting each of 6 Curtis algorithm criteria) as well as times to immediate and anytime switch and discontinuation. Times to discontinuation, switching or either will be assessed with Kaplan-Meier curves and Cox proportional hazards models. 8723 Compare All-Cause and RA-Related Health Care Utilization Between TOFA

8.7.2.3. Compare All-Cause and RA-Related Health Care Utilization Between TOFA Index Prescription OOP Costs and TNFi Cycling with ETN and ADA vs. TOFA Switching Cohorts

For this objective descriptive analysis will be conducted. All-cause and RA-related pharmacy and medical resource utilization measures (flags and 12-month counts) will be presented per patient during the 12-month baseline and follow-up periods. In addition, changes from baseline to follow-up will be evaluated.

8.7.2.4. Compare All-Cause and RA-Related Healthcare Costs Between TOFA Index Prescription OOP Costs and TNFi Cycling with ETN and ADA vs. TOFA Switching Cohorts

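### Out-of-pocket cost accumulated over follow-up months 1-12 is labelled a baseline characteristic and is left eligible as a covariate, although it depends heavily on how many fills the patient had

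*Combined protocol and SAP*

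**What the plan says.** Section 8.3 has one row for index-medication OOP costs, with one role, "Baseline Characteristic". Its definition says that these costs "will be identified for the first index medication rx and cumulative by month (1-12) of follow-up". The row counts pharmacy claims only ("only looking at pharmacy claims here noting index event is a prescription fill"). The same section defines follow-up: "The primary post-index period is 12 months including the index date". So the row combines a quantity known at index (the first fill) with one that accrues over the following year.

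Section 8.7.4 sets the covariate pool: "Variables listed in Section 8.3 will be considered for inclusion in the multivariable models". Within that pool, "specific predictors to be included will be determined based upon clinical rationale and statistical significance". No sentence confines candidates to variables measured by the index date.

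Persistence in Section 8.3 is derived from index-drug fills and administrations, with a gap of at least 60 days ending it. It is analysed by multivariable methods (Section 8.7.1.1), Cox models (Section 8.7.2.2) and logistic regression (Section 8.7.6). The high/low OOP exposure is defined on the index prescription only (Sections 7.1, 7.2 and 8.7.1.1).

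**The concern.** The role column is how the plan separates baseline variables from outcomes, and for the cumulative part of this row the role is wrong. Two patients with the same first-fill OOP will differ on this supposed baseline variable largely because one stayed on the drug longer.

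Conditioning on it would compare patients at equal cumulative spend. At equal spend, a patient who pays more per fill must have had fewer fills, so high OOP would appear to shorten persistence even if it had no effect. The same dependence reaches the switching models and the effectiveness proxy, whose adherence component is also computed from fills. In the cost models there is a part-whole problem as well: Section 8.3.1 counts patient-paid amounts in the cost outcome, so cumulative OOP is a component of what is being modelled.

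**Working it through.** The plan states no sample size, power or expected effect on this point, so there is no figure to reproduce. The check is an identity followed by illustrative simulation.

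**1. Identity.** Cumulative OOP at month 12 is the sum of OOP over the fills in that year. If OOP per fill is a constant p and there are N fills, cumulative OOP = p × N, and log(cumulative) = log(p) + log(N). Taking p = $128, a per-prescription figure for biologics in Section 6 used here only as an example:

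| Fills | Cumulative OOP |
|---|---|
| 1 | 128 × 1 = $128 |
| 3 | 128 × 3 = $384 |
| 6 | 128 × 6 = $768 |
| 12 | 128 × 12 = $1,536 |

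The dependence is strong but not complete. OOP per fill can vary, fills after a restart add cost but not persistence, and administrations of etanercept or adalimumab count towards persistence but not towards this pharmacy-only cost.

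**2. Simulation with no true OOP effect.** The following are assumed and not in the documents: exponential time to discontinuation with 45% persistent at day 360, 30-day fills, and lognormal OOP with log-SD 1.2. High and low are split at the median first-fill OOP. Persistence days are regressed on the high indicator by ordinary least squares, with and without 12-month cumulative OOP.

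| Model | High minus low (days) |
|---|---|
| Unadjusted | about 0 (-0.7 to +3.0) |
| Adjusted, OOP constant per fill, linear | about -25 |
| Adjusted, OOP constant per fill, log | about -159 |
| Adjusted, later fills independent of first, linear | about -3 to -19 |
| Adjusted, later fills independent of first, log | about -28 to -35 |
| Log cumulative and log first-fill OOP both included | near 0 |

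Shortening the window does not remove the bias. Adjusting for log cumulative OOP through month 3 only gave about -66 to -71 days.

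**3. Sensitivity.** This was run with constant OOP per fill, log form, 200,000 patients per scenario, 12-month persistence of 40-60% in the low-OOP group and log-SD 0.5-1.5.
- No true effect: the difference moved from about 0 to between -105 and -153 days, and the odds ratio for persistence from about 1.0 to 0.03-0.10.
- Hazard ratio 1.58 (the figure Section 6 cites for etanercept and adalimumab starters): the difference moved from between -32 and -44 days to between -114 and -181 days.
- Capping cumulative OOP at $2,000, with no true effect: -152 days.

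**4. Would selection on significance screen it out?** In simulated studies of 300 patients with no true OOP effect, log cumulative OOP was significant at 5% in all 500. The significance criterion would favour this variable.

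**The case against.** The strongest reply is that this is hypothetical. Section 8.7.4 says only that Section 8.3 variables will be considered. Section 8.3 also contains persistence, switching and effectiveness, so read literally the sentence would let outcomes predict themselves. It describes a loose pool, and clinical rationale could exclude cumulative OOP. This stands: the harm is conditional on a choice the plan permits but does not make. It does not dispose of the point, because those other variables carry the role of outcome, which warns the analyst off, whereas this one carries the opposite label.

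A reader might infer that Section 8.7.2.1 already nominates the follow-up total as a model input, since it mentions cumulative and index OOP costs among the characteristics examined for "differences between the cohorts that will inform multivariable analyses". The documents do not support that. Section 8.3 has two separate rows, for cumulative OOP from 1 January of the index year through index and for index-date OOP excluding the index drug. Section 8.7.2.1 most naturally means those, and it mentions index-medication OOP separately afterwards as something to be described.

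A reader might also infer that the primary OOP comparison is already biased. It is not: the exposure and the unadjusted contrast use the first fill only.

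On size, OOP includes a deductible, so constant OOP per fill is an extreme case, and the largest figures belong to it. Adding log first-fill OOP also brings the null estimate near zero. Both points stand, but the second is limited comfort. By the identity, first-fill and cumulative OOP together nearly reveal the number of fills (R-squared 0.87-0.92 for persistence days in the sensitivity runs), so such a model would tend to absorb a real effect too.

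Finally, a cohort that stops sooner did pay less over 12 months, so the descriptive total is not wrong.

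**Conclusion.** The role is wrong as written for the cumulative part of the row, and the covariate rule in Section 8.7.4 leaves that part eligible. If it were included, the direction of bias in the OOP contrast is predictable, but the size is not a single number. With no true effect, it runs from about -3 to -160 days under the main assumptions (45% persistent at day 360, 30-day fills, lognormal OOP with log-SD 1.2), according to how OOP varies across fills and the functional form. It is near zero if log first-fill OOP is also included. These figures show direction and order of magnitude only. The concern is confined to adjusted models of persistence, switching, effectiveness and cost. This should be corrected, but it does not invalidate the design.

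**What to change.** Split the Section 8.3 row. Keep first-fill OOP as the exposure/baseline variable, and relabel cumulative month 1-12 OOP as a post-index descriptive outcome. In Section 8.7.4, state that candidate covariates are limited to those measured on or before the index date, so that cumulative follow-up OOP is barred from the persistence, switching, effectiveness and cost models. Any variable defined after index that is deliberately kept should be named and justified. The combination-versus-monotherapy status is one, because it uses the 90 days from index.

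The cost is one table row and one or two sentences, and no planned description is lost. Reporting OOP per 30 days supplied alongside the total would help when comparing cohorts with different persistence, but it is optional.
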